5.1. Inclusion Criteria

Each potential participant must satisfy all of the following criteria to be enrolled in the study:

1. Signed informed consent prior to any study-mandated procedure.
2. Criterion modified per Amendment 2
 - 2.1 WHO FC II or III. Enrollment will be stratified by WHO FC II or III. Proportion of participants with WHO FC II and WHO FC III are expected to be approximately 40% and 60%, respectively.
3. Criterion modified per Amendment 2
 - 3.1 PAH etiology belonging to one of the following groups according to classification²⁷:
 - Idiopathic PAH
 - Heritable PAH
 - Drugs or toxins induced
 - PAH associated with connective tissue disease
 - PAH associated with congenital heart disease, with simple systemic-to-pulmonary shunt at least 1 year after surgical repair.
4. Criterion modified per Amendment 2
 - 4.1 Criterion modified per Amendment 3
 - 4.2 Diagnosis of PAH within 3 years prior to initiation of selexipag (Day 1), and most recent right heart catheterization (RHC) within 1 year prior to initiation of selexipag (Day 1) showing:
 - mPAP \geq 25 mmHg and
 - PA wedge pressure (PAWP) or LV end-diastolic pressure (LVEDP) \leq 15 mmHg and
 - PVR $>$ 5 WU (400 dyn.s.cm⁻⁵) and
 - RVSV \leq 60 mL as shown in RHC.
5. Criterion modified per Amendment 2
 - 5.1 Patients already receiving PAH-specific oral mono or dual therapy (ie, phosphodiesterase type 5 inhibitors (PDE-5i) or soluble guanylate cyclase stimulators (sGCs) and/or ERA) or patients who are not candidates for these therapies. If on oral PAH-specific therapy, treatment has to be stable (ie, no introduction of new therapies or changes in dose) for at least 90 days prior to both ICF signature and Day 1.
6. Criterion modified per Amendment 2
 - 6.1 Criterion modified per Amendment 3
 - 6.2 NT-proBNP \geq 300 ng/L (\geq 300 pg/mL; \geq 35.5 pmol/L) at screening. Note: If local assessment of BNP (instead of NT-proBNP) is used for eligibility, BNP measurement of \geq 50 ng/L (\geq 50 pg/mL; 14.4 pmol/L) will be considered as meeting the inclusion criterion.
7. Criterion modified per Amendment 2

7.1 Men or women ≥ 18 years (or the legal age of consent in the jurisdiction in which the study is taking place if greater than 18) and <65 years.

8. Criterion modified per Amendment 2

8.1 Criterion modified per Amendment 3

8.2 Women of childbearing potential (Section 10.5) must meet the following criteria:

- Have a negative serum pregnancy test during screening and a negative urine pregnancy test on Day 1, and
- Agree to use acceptable methods of contraception from Day 1 to at least 30 days after study intervention discontinuation (Section 10.5), and
- If only using hormonal contraception, have used it for at least 1 month (30 days) before Day 1, and
- Agree to perform monthly pregnancy tests to at least 30 days after study intervention discontinuation.

9. New criterion per Amendment 2

9.1 6MWD ≥ 150 m during screening period.

5.2. Exclusion Criteria

Any potential participant who meets any of the following criteria will be excluded from participating in the study:

1. Prior use of IP-receptor agonist, prostacyclin, or prostacyclin analog. Use of such treatments for vasoreactivity testing is not exclusionary; intermittent use of such treatments for digital ulcers or Raynaud's phenomenon is not exclusionary if stopped >6 months (180 days) prior to Day 1.
2. Treatment with strong inhibitors of CYP2C8 (eg, gemfibrozil) within 4 weeks (28 days) prior to Day 1.
3. Treatment with another investigational drug planned or taken within 12 weeks (84 days) prior to Day 1.
4. Cardiopulmonary rehabilitation programs based on exercise between informed consent and expected Week 26 visit date.
5. Criterion modified per Amendment 3
- 5.1 Decompensated cardiac failure requiring hospitalization, emergency room visit or intravenous (iv) diuretics in the 10 weeks (70 days) before Day 1, inclusive.
6. Severe coronary heart disease or unstable angina.
7. Cerebrovascular events (eg, transient ischemic attack, stroke) within 3 months (90 days) prior to Day 1.

8. Left atrial volume indexed for body surface area $\geq 43 \text{ mL/m}^2$, assessed by Echo or cardiac MRI.
9. Myocardial infarction within 6 months (180 days) prior to Day 1.
10. Criterion modified per Amendment 2
10.1 Body mass index $>40 \text{ kg/m}^2$ or body weight $<40 \text{ kg}$.
11. Criterion modified per Amendment 2
11.1 Presence of one or more of the following signs of relevant lung disease at any time up to Day 1 - **if pulmonary function test results are missing, then exclusion 11 is considered as met.**
 - Diffusing capacity of the lung for carbon monoxide $<40\%$ of predicted UNLESS computed tomography reveals no or mild interstitial lung disease
 - Forced vital capacity $<60\%$ of predicted^b
 - Forced expiratory volume in 1 second $<60\%$ of predicted^b.
12. Known or suspected pulmonary veno-occlusive disease (PVOD).
13. Congenital or acquired valvular defects with clinically relevant myocardial function disorders not related to pulmonary hypertension.
14. SBP $<90 \text{ mmHg}$ at screening or on Day 1.
15. Criterion modified per Amendment 3
15.1 Severe renal impairment (estimated glomerular filtration rate by Modification of Diet in Renal Disease [MDRD] formula $\leq 30 \text{ mL/min/1.73 m}^2$ or serum creatinine $>2.5 \text{ mg/dL}$ at screening) or ongoing or planned dialysis.
16. Criterion modified per Amendment 2
16.1 Criterion modified per Amendment 3
16.2 Known and documented severe hepatic impairment (with or without cirrhosis) at screening, defined as Child-Pugh Class C^c.
17. Known or suspected uncontrolled thyroid disease (hypo- or hyperthyroidism).
18. Criterion modified per Amendment 3
18.1 Any hospitalization within 10 weeks (70 days) prior to Day 1, inclusive (except elective hospitalizations for surgery or standard monitoring of pre-existing conditions that did not worsen).

^b Pulmonary function tests may be performed either with or without the use of bronchodilators, as per local clinical practice.

^c The assessment of hepatic impairment (Child-Pugh Score) must be fully documented for participants who have clinical signs and/or evidence (from central and/or local lab) of hepatic impairment. Absence of hepatic impairment must be documented in the source data as well.

19. Concomitant life-threatening disease with a life expectancy of less than 12 months.
20. Criterion modified per Amendment 3
 - 20.1 Hemoglobin <80 g/L (<8 g/dL; <4.96 mmol/L) at screening.
21. Hypersensitivity to selexipag or any study intervention excipient (mannitol, maize starch, hydroxypropylcellulose, magnesium stearate, hypromellose, propylene glycol, titanium dioxide, carnauba wax, iron oxide red, iron oxide yellow, iron oxide black).
22. Criterion modified per Amendment 2
 - 22.1 Pregnancy, breastfeeding, or intention to become pregnant during the study.
23. Any factor or condition likely to affect compliance with study intervention or visit plan, as judged by the investigator.
24. Claustrophobia.
25. MRI-incompatible permanent cardiac pacemaker, automatic internal cardioverter.
26. Metallic implant (eg, defibrillator, neurostimulator, hearing aid, permanent use of infusion device, dental brace, metal-containing tattoo ink)^d.
27. Criterion modified per Amendment 3
 - 27.1
 - Cardiac arrhythmia assessed severe by the investigator
 - Conditions that could interfere with proper cardiac gating, eg, atrial fibrillation, multiple premature ventricular or atrial contractions.

5.3. Lifestyle Considerations

Potential participants must be willing and able to adhere to the following lifestyle restrictions during the course of the study to be eligible for participation:

1. See Section 6.6 for details regarding prohibited and restricted therapy during the study.
2. Agree to follow all requirements that must be met during the study as noted in the inclusion and exclusion criteria (eg, contraceptive requirements, monthly pregnancy testing in Section 5.1).

5.4. Screen Failures

For participants who failed screening, the following data will be recorded in the eCRF if available: reason for screening failure and baseline data collected until confirmation of the screening failure.

^d Local MRI team's advice should be sought in case of doubt.

Individuals who do not meet the criteria for participation in this study (screen failure) may be rescreened once, if the reason for non-eligibility was transient (eg, abnormal laboratory test, insufficient wash-out period of an exclusionary medication). All screening assessments must have been made within 28 days before Day 1. Exceptional and limited retesting of abnormal screening values that lead to exclusion are allowed only once using an unscheduled visit to reassess eligibility during the screening period. If a participant does not meet all inclusion and exclusion criteria (is a screen failure) but at some point in the future is expected to meet the participant eligibility criteria, the participant may be rescreened on one occasion only. Participants who are rescreened will be assigned a new participant number, undergo the informed consent process, and then restart a new screening phase.

Participant Identification, Enrollment, and Screening Logs

The investigator agrees to complete a participant identification and enrollment log to permit easy identification of each participant during and after the study. This document will be reviewed by the sponsor study-site contact for completeness.

The participant identification and enrollment log will be treated as confidential and will be filed by the investigator in the study file. To ensure participant confidentiality, no copy will be made. All reports and communications relating to the study will identify participants by participant identification.

6. STUDY INTERVENTION

6.1. Description of Study Intervention

Manufacturing, labeling, packaging, and supply of study intervention will be conducted according to Good Manufacturing Practice, Good Clinical Practice, and any local or national regulatory requirements.

Selexipag will be manufactured and provided under the responsibility of the sponsor. See the Investigator's Brochure¹⁶ for a list of excipients.

All study intervention supplies are to be used only in accordance with this protocol and not for any other purpose.

Study intervention is labeled to comply with the applicable laws and regulations of the countries/territories in which the study sites are located. Labels must remain affixed to the bottles.

Open-label selexipag will be provided as round, debossed, film-coated tablets in childproof bottles.

Study intervention name:	Selexipag
Dosage formulation	Round, film-coated tablets

Unit dose strengths/ Dosage levels:	200 µg: light-yellow, film-coated tablets with “2” debossed on one side 400 µg: red, film-coated tablets with “4” debossed on one side 600 µg: light-violet, film-coated tablets with “6” debossed on one side 800 µg: green, film-coated tablets with “8” debossed on one side 1000 µg: orange, film-coated tablets with “10” debossed on one side 1200 µg: dark-violet, film-coated tablets with “12” debossed on one side 1400 µg: dark-yellow, film-coated tablets with “14” debossed on one side 1600 µg: brown, film-coated tablets with “16” debossed on one side
Route of administration	Oral
Dosing instructions	One dose twice daily (in the morning and in the evening), with or without food.

6.2. Study Intervention Administration

The tablets will be administered orally and should be swallowed whole (ie, not crushed, split, or chewed) with water.

On Day 1, the participant will receive only 1 dose, and at each dose change, the first intake of the new dose is to be taken in the evening to reduce the likelihood of the occurrence of prostacyclin-associated AEs. Tolerability may improve when study intervention is taken with food. Participants with moderate hepatic impairment (Child-Pugh Class B) or who are concomitantly taking (a) moderate CYP2C8 inhibitor(s) will start with 200 µg qd in the morning of Day 2.

For a definition of study intervention overdose, see Section [6.9](#).

Study intervention administration must be captured in the source documents and the eCRF. Study-site personnel will instruct participants on how to store study intervention for at-home use as indicated for this protocol.

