6.2.1. Study Intervention Up-Titration

Based on the GRIPHON study, the effect of selexipag on the composite endpoint of death from any cause or a complication related to PAH is consistent across different IMDs. The goal of the up-titration is to permit each participant to reach his/her personal highest tolerated dose without unmanageable prostacyclin-associated adverse effects.

Study intervention will be up-titrated to allow each participant to reach their IMD, in the range of 200 to 1,600 µg twice daily.

The study intervention will be up-titrated from Day 1 to the end of Week 12 (Day 84). Dosing will start at 200 µg twice daily. The site will call the participant once a week from the end of Week 1 to the end of Week 12 and decide whether to increase the dose by 200 µg twice daily ([Table 2](#)) if possible. Up-titration will be flexible and may be adapted in case of adverse effects that cannot be relieved with symptomatic treatment^e. In this case, the site may either postpone up-titration by 1 week or down-titrate study intervention.

^e Such as headache, diarrhea, nausea and vomiting, jaw pain, myalgia, pain in extremity, arthralgia, and flushing.

The dose reached at the end of Week 12 will be considered the participant's IMD and will be maintained until EOT.

Table 2: Up-Titration Guide

Weeks	Days	Target selexipag dose (µg, twice per day) ^a	Comments
1	1-7	200	In case of adverse effects that cannot be relieved with symptomatic treatment, postponement of up-titration by 1 week or down-titration should be considered.
2	8-14	400	
3	15-21	600	
4	22-28	800	
5	29-35	1000	
6	36-42	1200	
7	43-49	1400	
8	50-56	1600	
9-12	57-84	Buffer period to permit up/down-titration to ensure IMD is reached at the end of Week 12.	
13-52	85-364	IMD	

IMD individual maintenance dose

^a On Day 1, the participant will receive only 1 dose, and at each dose change the first intake of the new dose should be taken in the evening.

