6.7. Study Intervention Dose Modification

Any dose/dosage adjustment should be overseen by medically-qualified study-site personnel (principal or sub-investigator), unless an immediate safety risk appears to be present. See Section 6.2.1 for titration of study intervention during the first 12 weeks of treatment.

For participants with moderate hepatic impairment (Child-Pugh Class B) or using moderate inhibitors of CYP2C8 (eg, clopidogrel, deferasirox, teriflunomide, leflunomide) concomitantly with the study intervention, dosing frequency of study intervention must be reduced to once a day. Dosing

^f According to the study intervention administration log

frequency of selexipag should be reverted to twice daily when co-administration of moderate CYP2C8 inhibitor is stopped¹⁶.

It has been shown that, when moderate or strong inducers of CYP2C8 are used in combination with selexipag, the exposure to selexipag active metabolite is reduced by half. Dose adjustment of selexipag may be required with concomitant administration of inducers of CYP2C8 (eg, rifampicin, carbamazepine, phenytoin).

The effect of strong inhibitors of UDP-glucuronosyltransferase (UGT)1A3 and UGT2B7 (eg, valproic acid, probenecid, and fluconazole) on the exposure to selexipag or its active metabolite has not been studied. Concomitant administration may result in an increase in exposure to the active metabolite. Therefore, caution is required when these medicinal products are administered concomitantly with selexipag.

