6.9. Overdose

Overdose is defined by the intake of a dose $>1,600 \mu\text{g}$ or a total daily dose $>3,200 \mu\text{g}$. For participants with moderate hepatic impairment or who are concomitantly taking moderate CYP2C8 inhibitor(s), the dosing frequency is once daily and overdose is defined by the intake of a dose $>1,600 \mu\text{g}$ or a total daily dose $>1,600 \mu\text{g}$.¹⁶

Isolated cases of overdose up to $3,200 \mu\text{g}$ were reported. Mild, transient nausea was the only reported consequence. In the event of overdose, supportive measures must be taken as required.

In the event of a selexipag overdose, the investigator or treating physician should:

- Contact the Medical Monitor immediately.

- Evaluate the participant to determine, in consultation with the Medical Monitor, whether study intervention should be interrupted or whether the dose should be reduced.
- Closely monitor the participant for AE/SAE and laboratory abnormalities until selexipag can no longer be detected systemically (at least 3 days).
- Document the quantity of the excess dose as well as the duration of the overdosing in the eCRF.
- Institute supportive therapy as clinically indicated. Dialysis is unlikely to be effective because selexipag and its active metabolite are highly protein bound.

For more information see Section 10.4.

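### The evening rule for dose changes and the twice-daily titration table are not reconciled with the once-daily regimen that some participants must follow and start in the morning

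*Protocol*

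**What the plan says.** **Evening rule.** Section 6.2 states it for every dose change: "at each dose change, the first intake of the new dose is to be taken in the evening to reduce the likelihood" of prostacyclin-associated events. Footnote a to Table 2 in Section 6.2.1 repeats it: "at each dose change the first intake of the new dose should be taken in the evening". Neither place has an exception.

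**Titration text.** Section 6.2.1 asks the site each week to "decide whether to increase the dose by 200 µg twice daily". The dose column of Table 2 is headed "Target selexipag dose (µg, twice per day", and the maintenance range of 200 to 1,600 µg is also given for twice-daily dosing. No once-daily version appears.

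**Once-daily participants.** The Section 6.2 paragraph that holds the evening rule also starts participants with Child-Pugh Class B or on a moderate CYP2C8 inhibitor on 200 µg "qd in the morning of Day 2". Section 6.7 says that for them "dosing frequency of study intervention must be reduced to once a day".

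**Overdose.** Section 6.9 sets the general limits at more than 1,600 µg per intake or more than 3,200 µg per day. For the group above, "the dosing frequency is once daily and overdose is defined by the intake of a dose" above 1,600 µg or a daily total above 1,600 µg.

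The group can be enrolled: Section 5.2 excludes only Child-Pugh Class C (criterion 16.2) and strong CYP2C8 inhibitors (criterion 2).

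**The concern.** The evening rule suits someone who already takes a dose every evening: the evening dose is simply replaced by the higher one. A participant who takes one dose each morning has no evening dose to replace. The protocol does not say whether that day's morning dose is still taken, or whether later doses stay in the evening or return to the morning.

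A site must therefore choose. One choice gives two intakes in a day to someone whom 6.7 restricts to one. The other leaves out a morning dose. Different sites may choose differently. If the first choice is repeated at higher dose levels, the day's total can pass the 6.9 limit. The site must then contact the Medical Monitor immediately (6.9), and the event counts as a special reporting situation (10.4.4). The issue is a safety instruction that does not fit the group it reaches, not the sample size or the endpoint.

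**Working it through.** **Inputs**
- Dose levels: 200, 400, 600, 800, 1000, 1200, 1400 and 1600 µg, so 8 levels and 7 upward steps (Table 2). The table is written for twice-daily dosing; using it for once-daily dosing is an assumption.
- Daily limits: 3,200 µg in general, 1,600 µg for once-daily participants (6.9).
- Once-daily start: in the morning (6.2).
- First intake of each new dose: in the evening (6.2, Table 2 footnote a).
- Morning and evening intakes are taken to be about 12 hours apart (assumption).

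**1. The protocol's own limits.** Top dose × intakes per day gives 2 × 1,600 = 3,200 µg and 1 × 1,600 = 1,600 µg. Both match 6.9.

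**2. Twice-daily participants.** With old dose D in the morning and D + 200 in the evening, the change-day total is 2D + 200. Over the 7 steps this runs from 600 to 3,000 µg. None exceeds 3,200, so the rule fits this regimen.

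**3. Once-daily participants, reading (a): the morning dose is taken, the new dose follows that evening, and morning dosing resumes after each change.** The formula is the same, but the limit is 1,600 µg.

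| Step (µg) | Change-day total (µg) | Above 1,600? |
|---|---|---|
| 200 to 400 | 600 | no |
| 400 to 600 | 1000 | no |
| 600 to 800 | 1400 | no |
| 800 to 1000 | 1800 | yes |
| 1000 to 1200 | 2200 | yes |
| 1200 to 1400 | 2600 | yes |
| 1400 to 1600 | 3000 | yes |

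Four of 7 steps exceed the limit, and every change day has two intakes.

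**4. Reading (b): the morning dose is skipped on the change day.** The calendar-day total is the new dose alone, at most 1,600 µg, so 0 of 7 steps exceed the limit. The gap from the previous morning to that evening is 24 + 12 = about 36 hours. It is followed by about 12 hours if morning dosing resumes.

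**5. Reading (c): dosing stays in the evening after the first change.** If the morning dose is taken on the first change day, the total is 200 + 400 = 600 µg, with two intakes about 12 hours apart. If it is skipped, the gap is about 36 hours. Every later change is evening to evening, with one intake a day. None of the 7 steps exceeds 1,600 µg, and only one interval is irregular.

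Under every reading, at least the first change from a morning dose brings either two intakes in a day or a gap of about 36 hours.

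**The case against.** The strongest reply is that one reading satisfies every cited section. Skipping the morning dose and taking the new dose that evening gives one intake that day, in the evening, within 1,600 µg. The protocol sets no hourly interval for once-daily dosing, and the restart rule in 7.2 begins only at an interruption of 3 days. Section 6.7 is also the specific and mandatory text for this group, and it requires medically qualified oversight of dose adjustments. Much of this stands: the text does not force a breach of 6.7 or 6.9. But no section tells the site to skip a dose or says when the following dose is due. Section 6.7 rules out two intakes without saying how an evening first intake is then to be reached.

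A reader might infer that the protocol as written schedules overdoses for this group at 4 of 7 steps. The documents do not support that. They fix only the morning start, not continued morning dosing, and they do not say that the morning dose is taken on a change day or that the twice-daily levels apply once daily. Reading Table 2 literally as two intakes a day (2 × 1,000 = 2,000 µg at the 1000 µg level) would mean ignoring 6.7.

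A reader might also infer a particular pharmacological vulnerability. Section 6.7 gives no reason for the once-daily frequency; its remarks on exposure concern other classes of drug.

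Two limits on reach also stand. The documents do not say how many participants dose once daily, and the SAP (Sections 1 and 5.3.2) reports premature termination with a very small number of participants.

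**Conclusion.** The point holds as an inconsistency in dosing instructions that bears on safety. The evening rule is stated without exception and the titration table is written for twice-daily dosing only, while the same protocol requires a once-daily regimen, started in the morning, for a group it allows to enrol.

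The firm part is that, for a once-daily participant dosed in the morning, at least the first dose change means two intakes in a day, contrary to 6.7, or a skipped morning dose with a gap of about 36 hours.

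The conditional part is the overdose limit. The change-day total exceeds it at 4 of 7 steps (1800, 2200, 2600 and 3000 µg) only if all three of these hold: the 200 to 1,600 µg levels are used once daily, the old dose is taken on the morning of each change, and morning dosing resumes afterwards. If dosing stays in the evening after the first change, the count is 0 of 7. The range is therefore 0 to 4 of 7, depending on a choice the protocol leaves open.

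The primary analysis and the sample size are not affected.

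**What to change.** Reconcile Section 6.2, Section 6.2.1 with Table 2 (increment, range, column heading and footnote a), Section 6.7 and Section 6.9 for once-daily participants. The text should state whether and how the evening rule and the titration table apply to them. The evening rule is repeated in the protocol synopsis, in protocol Section 4.1 and in SAP Section 1.2, so those places should be aligned too. Which rule or dose is right is for the sponsor's clinical team.

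The cost is a footnote and a sentence or two, with no effect on twice-daily participants or on any analysis. Because the study ended early, the practical gain is limited.
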